In the IFCT-0002 trial [25], including 528 patients with stage I and II NSCLC, 91.6% of patients achieved complete resections. In the other trials this rate was lower (see table) but with smaller number of patients, more advanced stages and also older studies. For all these reasons and because this trial is in continuity with IFCT 0002 trial, we decided to take 90% as the threshold below which the rate of complete oncologic resection observed was unacceptable.

Durvalumab is a novel IgG1-kappa PD-L1 inhibitor with potent and specific binding to PD-L1 at picomolar concentrations, with directed mutations in the Fc region, limiting off-target cytotoxicity in PD-L1-expressing immune cells [26]. Durvalumab has been shown to increase T-cell activation *in vitro* by blocking PD-L1/PD-1 engagement [26] and induces antitumor responses in tumor-bearing mice, with corresponding changes in peripheral immune markers [26]. Durvalumab has also been shown to inhibit tumor growth *in vivo* xenograft models [26].

In advanced NSCLC, inhibition of the PD-1 immune checkpoint pathway has been shown to induce durable clinical responses across all histologies and is therefore of broad clinical relevance. durvalumab has a favorable safety profile and limited off-target T cell effects and has good pharmacokinetic and pharmacodynamic properties. Results of early trials with durvalumab in advanced cancers are consistent with a class effect of early and sustained tumour control that has been observed previously with other inhibitors of the PD-1 immune checkpoint pathway. durvalumab is particularly attractive as a therapeutic strategy in the adjuvant setting as it may generate immunologic memory and persistent activity in memory B cells, allowing for active and sustained surveillance and killing of tumour cells and possibly long term cure. NSCLC patients with PD-L1 expression positive resected tumours may be particularly sensitive to immunotherapy with durvalumab given accumulating evidence in patients with advanced disease. Even if the primary endpoint is the complete resection for early stage, the expected benefit is to obtain a signal in term of response and increase of disease free survival.

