Durvalumab has been shown to have a favourable pharmacokinetic (PK) profile that exhibits nonlinear PK at doses up to 1.0 mg/kg, with dose-dependent increases in target engagement and target suppression at doses ≥ 0.3 mg/kg every two weeks [22]. Immune-related reactions that are possible with this class of drug (e.g. enterocolitis, dermatitis, hepatotoxicity, endocrinopathy, pneumonitis) have been reported in less than 5% of patients on durvalumab. To date, there have been no cases of infusion reaction or IgE-induced allergic reactions with durvalumab.

Study Hypothesis: A theoretical feasibility rate equal to or lower rate of complete resection than $P_0=85\%$ is considered as unacceptable after immune treatment. A test for single binomial proportion for a two-stage design with a 1:1 randomization and O'Brien-Fleming (OF) stopping rules will be used. $P_0 = 85\%$ $P_1 = 95\%$ Power = 90% and α risk (one-sided) = 5%. Based on these assumptions, 81 patients are required.

Table 1: Neoadjuvant trials with number of patients considered with complete resection

Trial	First author	Reference	Stage	N Neoadjuvant arm	N Surgery (%)*	N Exploratory thoracotomy	N Surgery for complete resection (%)*	N Complete resection (%)*
MIP91	Depierre	[27]	IB	187	167 (89,3)	5	162 (86,6)	ND
			II					
			IIIA					
S9900	Pisters	[28]	IB	169	152 (89,9)	5	147 (86,9)	142 (84)
			II					
			IIIA non N2					
NATCH	Felip	[29]	IA >2cm	201	181 (90)	7	ND	ND
			IB					
			II T3N1					
CHEST	Scagliotti	[30]	IB	129	110 (85,2)	ND	ND	97 (75,1)
			II					
			T3N1					
IFCT 0002	Westeel	[25]	I, II	528	509 (96,4)	4	505 (95,6)	484 (91,6)

* % has been calculated in intention to treat (ITT), i.e. using the number of patients included in the neoadjuvant arm of the corresponding trial.

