15.2 Sample Size, Power

The maximum sample size (N) is calculated based on α , β , and the expected effect size, using a test for single binomial proportion for a two-stage design with a 1:1 randomization and O'Brien-Fleming (OF) stopping rules, allowing for early stopping for futility after Stage I. The software East 6.0 was used.

The rate of complete resection equal to or lower than 85% (P0) is considered as unacceptable after immune treatment. On the other hand, we can conclude to a good rate of complete resection if it is 95% (P1). The computation is based on the following assumption, considering the probability of compliance: P0 =85%; P1 = 95%; statistical power of 0.90; type I error rate (one-sided) of 0.05.

The null hypothesis that the rate of complete resection is P0 = 85% will be tested against a one-sided alternative. In the first stage, 39 patients will be accrued. If there are 34 or fewer responses in these 39 patients, the study will be stopped for futility. Otherwise, 38 additional patients will be accrued for a total of 77. The null hypothesis will be rejected if 71 or more responses are observed in 77 patients. To take into account 5% of ineligible patients, 81 patients will be included.

Duration of accrual: 18 months and 1 year follow-up.

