15.3 Analysis population

- The population of tolerance is defined as all patients who received one dose of treatment

- The population the intent to treat (ITT) will include all patients included
- The population of eligible patients will consist of ITT patients presenting no deviation judged major on the criteria for inclusion and non-inclusion

The deviations to the protocol will be reviewed by the principal investigators and then classified into minor or major deviations, and listed.

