15.4 Study Endpoints and Analysis

The primary endpoint will be performed on all eligible patients based on patient percentage surgical resection R0 after a maximum of 3 cycles of chemotherapy. It will be presented associated with confidence interval of 95%.

DFS is a secondary endpoint, defined as the time from the date of inclusion to the date of first documented disease relapse or the occurrence of a new invasive primary malignancy or death from any cause. Patients who are alive and disease/new invasive primary malignancy-free at the time of each analysis will be censored at their last disease assessment date.

OS is a secondary endpoint, defined as the time from the inclusion to the date of death of any cause, or censored at their last known alive date. All analysis on DFS will be carried out for the OS endpoint.

The analysis of secondary endpoints will be performed on patient eligible.

Although PD-L1 expression as measured by immunohistochemistry is hypothesized to be a potential predictive marker, this is as yet not validated in either the adjuvant or palliative settings. Further, the cut-off defining PD-L1 positivity has not been validated. This trial will also explore the utility of PD-L1 as a predictive biomarker as well as the optimal cut-off for positivity.

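### The benchmark resection rates count all included patients, but the trial's R0 rate counts eligible patients only and no analysis uses the ITT set, so the two can differ by the share dropped as ineligible

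*Protocol*

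**What the plan says.** **Benchmark.** In Protocol section 1.2 the rationale cites the sponsor group's earlier trial, in which "91.6% of patients achieved complete resections", and sets a threshold of 90% by reference to it. The footnote to Table 1 says that each percentage "has been calculated in intention to treat (ITT), i.e. using the number of patients included in the neoadjuvant arm" of the trial concerned.

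**Tested limit.** Section 15.2 states: "The rate of complete resection equal to or lower than 85% (P0) is considered as unacceptable after immune treatment". P1 is 95%, with "statistical power of 0.90; type I error rate (one-sided) of 0.05". For stage 1: "If there are 34 or fewer responses in these 39 patients, the study will be stopped for futility". The final rule requires at least 71 R0 resections in 77 patients. Inclusion is raised to 81 to allow for 5% ineligible patients.

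**Analysis sets.** Section 15.3: "The population the intent to treat (ITT) will include all patients included". The eligible set is the ITT set without patients who have a major deviation on the inclusion or non-inclusion criteria. The principal investigators make that classification.

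**Use of the sets.** Section 15.4: "The primary endpoint will be performed on all eligible patients based on patient percentage surgical resection R0". Secondary endpoints also use eligible patients. Safety (section 15.5) uses patients with at least one dose. The ITT set serves only as the starting point for the eligible set.

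**The concern.** In a single-arm trial there is no concurrent control group that loses patients by the same exclusion. The observed rate gets its meaning from outside figures, so it should be built in the same way as they are. Here the outside figures keep every included patient and the trial's own figure does not.

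Several eligibility criteria concern stage and local extent of disease (section 5.1). Patients wrongly included on those grounds might be completely resected less often, and dropping them would then raise the reported rate relative to Table 1.

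The trial is also unblinded, and section 15.3 does not say that deviations are classified before the resection result is known. Section 10.1 adds that patients who have had only a segmentectomy or wedge resection are not eligible. That label can only be applied after surgery, and it is not among the criteria of sections 5.1 and 5.2. At stake is whether a reader can set the reported R0 rate beside Table 1 without being misled.

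**Working it through.** **Inputs from the Protocol.** P0 = 0.85 and P1 = 0.95. Stage 1 continues with at least 35 of 39; success is at least 71 of 77; 81 patients are included; 5% are ineligible (15.2). Table 1 gives 484 complete resections among 528 included and 509 operated patients (1.2).

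**Assumption.** q is the R0 rate in ineligible patients. The Protocol does not give it, so the full range of 0% to 100% is shown.

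**1. Reproduce the design.** With eligible-set rate p, the success probability is the sum over x = 35 to 39 of P(X1 = x) × P(X2 ≥ 71 − x), where X1 ~ Bin(39, p) and X2 ~ Bin(38, p).
- p = 0.85: 0.042.
- p = 0.95: 0.895.

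These agree with the stated 0.05 and, near enough, with the stated 0.90.

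**2. Confirm the benchmark denominator.** 484/528 = 91.7% (printed as 91.6), so the printed figure uses included patients. On operated patients it would be 484/509 = 95.1%.

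**3. Gap between the two rates.** ITT rate = 0.95p + 0.05q, so eligible rate − ITT rate = 0.05(p − q).

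| p | q = 0% | q = 50% | q = p | q = 100% |
|---|---|---|---|---|
| 85% | +4.25 points | +1.75 | 0 | −0.75 |
| 95% | +4.75 points | +2.25 | 0 | −0.25 |

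**4. A bare success re-expressed.** 71/77 = 92.2% (exact 95% CI 83.8 to 97.1). There are 81 − 77 = 4 planned ineligible patients.
- None of the 4 is R0: 71/81 = 87.7% (78.5 to 93.9).
- 2 of the 4 are R0: 73/81 = 90.1% (81.5 to 95.6).
- All 4 are R0: 75/81 = 92.6% (84.6 to 97.2).

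**5. Success probability when the true ITT rate is 85%.** The eligible rate is p = (0.85 − 0.05q)/0.95, which goes into the formula of step 1.

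| Assumed q | Eligible rate p | P(success) |
|---|---|---|
| 0% | 89.5% | 0.27 |
| 50% | 86.8% | 0.10 |
| 85% | 85.0% | 0.042 |
| 100% | 84.2% | 0.029 |

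**The case against.** The case for leaving the plan alone has real weight.

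**The main ITT feature is kept.** Section 15.3 removes only patients with major eligibility deviations. Eligible patients who progress, refuse surgery or prove unresectable remain as failures. A reader might infer a gap like that between included and operated patients (91.7% against 95.1% in step 2). The definitions do not support that.

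**No formal comparison with Table 1 is planned.** The test is against a fixed 85%. The threshold that section 1.2 draws from the earlier trial is 90%, and nothing in the Protocol derives 85% from Table 1. A reader might infer that the test itself is invalid. It is not: for the eligible population it holds its level (0.042).

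**The direction is not shown.** A reader might infer that the result is biased upward. The Protocol gives no R0 rate in ineligible patients. Section 6 has imaging reports sent in before inclusion and reviewed if eligibility is in doubt, which should limit stage errors. Many other criteria, such as TSH, bilirubin or recent vaccination, have no obvious link to resection margins. Above q = 85% the effect reverses.

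**The choice is deliberate.** The sample size was inflated for it, and an additional ITT table could be left to an analysis plan.

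All of this limits the size and certainty of the point. It does not remove it, because the Protocol itself fixes the analysis set on one basis and explains its benchmark on another.

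**Conclusion.** The concern holds in a limited form. The benchmark rates are ITT rates, the primary and secondary endpoints are analysed on eligible patients only, and the ITT set has no assigned use. The mismatch is confined to the planned 5% dropped for major eligibility deviations.

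The possible distortion is lopsided: up to about 4.8 points upward against at most about 0.8 downward, compared with a P1 − P0 distance of 10 points. The upper figure needs every ineligible patient to fail and an eligible rate of 95%. All figures rest on 5% ineligible patients and on an assumed R0 rate among them. If more than 5% are dropped, the gap widens in proportion.

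This is a matter of comparability and of protection against classification made with the result in view. It is not an error in the decision rule.

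**What to change.** Add to Protocol section 15.4:

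> *The R0 rate with its 95% CI is also reported on the ITT population of 15.3, counting every included patient without R0 resection as a failure; comparisons with the Table 1 rates use this ITT rate. Major eligibility deviations are classified without knowledge of the resection result.*

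Keep the two-stage test against 85% on eligible patients as the only decision rule. Do not add a second significance test on ITT. An exact one-sided 5% test on 81 patients would need 75 R0 resections, so a bare success of 71/77 would pass only if all 4 ineligible patients were R0. With an eligible rate of 95% and q = 60%, the chance of passing both tests falls to 0.70, from 0.895 for the planned rule.

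The cost is one extra table row from data already collected, a supporting rate that may look less favourable, and a review of deviations arranged so that the resection result is withheld.

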15.5 Safety Monitoring

All patients who receive at least one dose of MEDI4376 will be included in the safety analysis. Descriptive summary tables will be presented on safety parameters

Immune adverse events of special interest will be analysed including: pneumonitis, endocrinopathies, dermatologic (rash/pruritus) and hepatic (elevation of transaminases/bilirubin).

The number of post-operative events and a tolerance report will be achieved on the first 15 patients to discuss the pursuit of the trial.

A definitive discontinuation of the study in real time is planned in case of occurrence of a new death (any cause combined) occurring within 90 days of the intervention among the 12 consecutive first patients enrolled after the resuming of the trial (46th patient and the following).

Tolerance data (90-day postoperative follow-up) for these 57 patients will be analyzed by the steering committee.

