Important medical events that may not be immediately life-threatening or result in death or hospitalization but may jeopardize the patient or may require intervention to prevent one of the other outcomes listed in the definition above should also usually be considered serious. Examples of such events include allergic bronchospasm requiring intensive treatment in an emergency room or at home, blood dyscrasias or convulsions that do not result in inpatient hospitalization, or the development of drug dependency or drug abuse.

A diagnosis of cancer during the course of a treatment should be considered as medically important. The List of Critical Terms (1998 adaptation of World Health Organization Adverse Reaction Terminology Critical Terms List, provided in the “Instructions for completing the ‘Serious Adverse Event/Expedited Report from a Clinical Trial’ form”) should be used as guidance for adverse events that may be considered serious because they are medically important.

Clarification of the difference in meaning between “severe” and “serious”

The term “severe” is often used to describe the intensity (severity) of a specific event (as in mild, moderate, or severe myocardial infarction); the event itself, however, may be of relatively minor medical

significance (such as severe headache). This is not the same as “serious”, which is based on the outcome or action criteria usually associated with events that pose a threat to life or functioning. Seriousness (not severity) serves as a guide for defining regulatory reporting obligations.

SAEs/AEs will be reported up to one month after surgery, and SAEs notification will be made within 24 hours.

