12.2 Period of Observation

For the purposes of this study, the period of observation for collection of adverse events extends from the date of signature of the informed consent until 100 days after the last day of study treatment except for adverse events related to study drug, which must be reported during follow-up period until resolution or initiation of further anti-tumor therapy.

If an Investigator detects a serious adverse event in a study subject after the end of the period of observation, and considers the event possibly related to prior study treatment, he or she should contact the Sponsor to determine how the adverse event should be documented and reported.

At each visit/assessment AEs will be assessed from information collected from the source documents and information transcribed into the CRF.

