12.3 Documentation and Reporting of Adverse Events by Investigator

All adverse events that occur during the observation period set in this protocol must be documented on the pages provided in the case report form in accordance with the instructions for the completion of adverse event reports in clinical studies. These instructions are provided in the case report form itself.

The following approach will be taken for documentation:

- All adverse events (whether serious or non-serious, or considered as an alert term) must be documented on the “Adverse Event” page of the case report form.
- If the adverse event is serious, the investigator must complete, in addition to the “Adverse Event” page in the case report form, a “Serious Adverse Event/Expedited Report from a Clinical Trial” form at the time the serious adverse event is detected.

This form must be faxed to the IFCT’s Pharmacovigilance department.

Every attempt should be made to describe the adverse event in terms of a diagnosis. If a clear diagnosis has been made, individual signs and symptoms will not be recorded unless they represent atypical or extreme manifestations of the diagnosis, in which case they should be reported as separate events. If a clear diagnosis cannot be established, each sign and symptom must be recorded individually.

All patients who have adverse events, whether considered associated with the use of the investigational products or not, must be monitored to determine the outcome. The clinical course of the adverse event will be followed up according to accepted standards of medical practice, even after the end of the period of observation, until a satisfactory explanation is found or the investigator considers it medically justifiable to terminate follow-up. All questions on the completion and supply of adverse event report forms and any further forms issued to the investigator at a later date to clarify unresolved issues should be addressed to the IFCT.

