12.4 Immediate Reporting by Investigators to IFCT

Serious adverse events and adverse events that fulfil a reason for expedited reporting to Pharmacovigilance must be documented on a “Serious Adverse Event/Expedited Report from a Clinical Trial” form in accordance with the “Instructions for completing the ‘Serious Adverse Event/Expedited Report from a Clinical Trial’ form”. This form must be completed and supplied to the Sponsor within 24 hours or at the latest on the following working day. The “Serious Adverse Event/Expedited Report from a Clinical Trial” form and the instructions are provided in the investigator’s study file.

The initial report must be as complete as possible, including details of the current illness and (serious) adverse event, and an assessment of the causal relationship between the event and the investigational product(s). The report will be completed in the electronic case report form. In case of unavailability of the CRF, a paper report will be sent by e-mail to [contact]. An acknowledgment of receipt will be sent to the site.

Information not available at the time of the initial report (e.g., an end date for the adverse event or laboratory values received after the report) must be documented on a follow-up “Serious Adverse Event/Expedited Report from a Clinical Trial” form.

The “Instructions for completing the ‘Serious Adverse Event/Expedited Report from a Clinical Trial’ form” give more detailed guidance on the reporting of serious adverse events, adverse events that comply with alert terms, and adverse events initially reported as non-serious that become serious. In the latter situation, when a non-serious event becomes serious, details must be forwarded immediately to the Sponsor on a “Serious Adverse Event/Expedited Report from a Clinical Trial” form.

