15 STATISTICAL CONSIDERATIONS

15.1 Objectives and Design

This is a multi-centre, prospective unblinded, single-arm phase II trial of the human monoclonal antibody directed against programmed cell death ligand-1 (PD-L1) durvalumab in neoadjuvant treatment in primary resectable stage IB (only T = 4 cm in greatest dimension, N0), stage IIA (T2b,N0) and some of stage IIB : (T1-2,N1) and (T3 : > 5 cm and \leq 7 cm in greatest dimension surrounded by lung or associated with separate tumor nodule(s) in the same lobe but without mediastinum or chest wall involvements, or superior sulcus tumors, N0) non-small cell lung cancer patients.

The primary objective is surgical resection R0 after maximum 3 cycles of immune therapy.

Secondary objectives will evaluate study treatment effect:

- Response Rate (RECIST 1.1) and metabolic response rate on TEP-FDG
- Tolerance and Post-operative adverse events (30 days after surgery)
- Delay between surgery and start of treatment
- Evaluation of predictive/prognostic significance of PD-1/PD-L1 expression
- Disease Free Survival (DFS)
- Overall survival (OS)
- Evaluation of changes in plasma/serum cytokines and other biomarkers before and after treatment
- Major Pathological Response on surgical tissue

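### Two conflicting AE/SAE reporting windows, neither tied to the 90 post-operative days that the section 15.5 death rule needs

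*Protocol*

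**What the plan says.** **The rule.** Section 15.5 stops the study definitively, as soon as it happens, for a "new death (any cause combined) occurring within 90 days of the intervention among the 12 consecutive first patients enrolled" after the restart, counting from the 46th patient. It then adds: "Tolerance data (90-day postoperative follow-up) for these 57 patients will be analyzed by the steering committee". I read the intervention as surgery, because this second sentence counts post-operative days.

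**The reporting windows.**
- Section 12.1.1, last sentence: "SAEs/AEs will be reported up to one month after surgery, and SAEs notification will be made within 24 hours".
- Section 12.2 runs collection from consent "until 100 days after the last day of study treatment except for adverse events related to study drug", which are reported for longer. After that period, the investigator contacts the sponsor about an SAE only if it is considered possibly related to study treatment.
- Section 12.3: "All adverse events that occur during the observation period set in this protocol must be documented". It also follows the course of events "even after the end of the period of observation, until a satisfactory explanation is found".
- Section 12.4 sets the SAE form deadline: "within 24 hours or at the latest on the following working day".
- Section 15.1 lists a secondary objective as "Tolerance and Post-operative adverse events (30 days after surgery".

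**The visits.** Sections 9.2 and 13.5 and Appendix I place post-operative visits at 4 weeks, 6 months and one year.

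**The concern.** A rule that ends the trial on one death works only if that death is notified promptly. The rule counts deaths from any cause up to post-operative day 90, but neither reporting window is defined by that day, and the two windows disagree with each other.

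A site can comply with the one-month sentence, which also carries the 24-hour SAE duty and agrees with the 30-day post-operative endpoint in section 15.1. It would then have no stated duty to notify a new, unrelated death on, say, day 45. The next scheduled contact is at 6 months. Patients could go on being enrolled and treated after the stopping criterion had been met, and the steering committee could review the 57 patients with incomplete 90-day data.

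**Working it through.** **The plan's own figure.** Twelve consecutive patients from the 46th: 46 + 12 − 1 = 57. This matches section 15.5.

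**Inputs.** Surgery 2 to 14 days after the last infusion (section 10.1). Infusions at weeks 0, 2 and 4 (section 8.1). First infusion within 7 days of inclusion (section 5.1). Horizon of 90 days (section 15.5). Accrual of 81 patients in 32 months (section 16.4.1) or 18 months (section 15.2).

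**Cover under the 100-day window.** With surgery *g* days after the last infusion, cover ends on post-operative day 100 − *g*, and the shortfall is max(0, *g* − 10).

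| *g* (days) | Cover ends, post-operative day | Shortfall against day 90 |
|---|---|---|
| 2 | 98 | 0 |
| 10 | 90 | 0 |
| 11 | 89 | 1 |
| 14 | 86 | 4 |

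Beyond the 14-day limit each day of delay adds one day: the shortfall is 11 at *g* = 21 and 18 at *g* = 28.

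**Cover under the one-month sentence.** 90 − 30 = 60 days uncovered (59 to 62 for a month of 31 to 28 days). The two windows end 86 − 30 = 56 to 98 − 30 = 68 days apart.

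**Longest delay under the one-month sentence.** If nothing reveals the death before the 6-month visit (183 days): 183 − 90 = 93 days for a death on day 90, and 183 − 31 = 152 days for a death on day 31.

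**Enrolment during that delay.** These are ceilings, with constant accrual assumed.
- Rates: 81/32 = 2.53 and 81/18 = 4.5 per month of 30.44 days.
- Inclusion to surgery: 28 + 2 = 30 days at the shortest and 7 + 28 + 14 = 49 at the longest. Inclusion to death is therefore 61 to 80 days (death on day 31) or 120 to 139 days (death on day 90).
- Already entered after the index patient by then, at 4.5 per month: 9.0 (61 days), 11.8 (80), 17.7 (120), 20.6 (139).
- Entering during the delay, for index patient *k*: min(rate × delay, 81 − *k* − already entered).

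| Case | Calculation | Patients |
|---|---|---|
| 2.53 per month, 93 days, any *k* from 46 to 57 | 2.53 × 93/30.44 | 7.7 |
| 4.5 per month, 152 days, *k* = 46 to 49 | 4.5 × 152/30.44 | 22.5 |
| 4.5 per month, 152 days, *k* = 50 | 81 − 50 − 9.0 | 22.0 |
| 4.5 per month, death on day 31, *k* = 57 | 24 − 11.8 to 24 − 9.0 | 12.2 to 15.0 |
| 4.5 per month, death on day 90, *k* = 57 | 24 − 20.6 to 24 − 17.7 | 3.4 to 6.3 |

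If enrolment were held at 57 for the review, which section 15.5 does not state, the most is for *k* = 46 with a death on day 31. At 2.53 per month 5.1 patients have already entered in 61 days, leaving 57 − 46 − 5.1 = 5.9. At 4.5 per month it is 57 − 46 − 9.0 = 2.0. Later index patients fall to 0.

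**Would a day-90 check be enough alone?** No. A death on day 31 could go unseen by schedule for 90 − 31 = 59 days, in which 4.9 to 8.7 patients would enter at the two rates.

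**The case against.** The strongest reply is that section 12.2 should govern. It is the section on the period of observation, and section 12.3 ties documentation to that period. On that reading the gap is 0 to 4 days, and every large figure depends on the weaker sentence. This is right as to likelihood. But the one-month sentence is current text, nothing ranks the two, and a site that follows it is complying with the protocol.

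Second, section 15.5 itself calls for 90-day follow-up of the 57 patients, so it can be read as requiring those data whatever the general window says. That supports the intent, but it supplies no contact, form or deadline. Case report form instructions that are not shown might do so.

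Third, the 4-day figure is conditional. It takes study treatment to mean durvalumab, which section 13.3 supports, and surgery on schedule. If surgery counted as study treatment there would be no gap. If surgery waited for adverse events to recover, as section 10.1 requires, the gap could be larger. Both qualifications stand.

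Fourth, other routes may reveal a death sooner. Reported events are followed to outcome, drug-related events stay reportable, possibly related late SAEs prompt contact with the sponsor, and the sponsor visits sites regularly (section 16.1.2). AEs are also collected at 6 months. These narrow the failure, but none gives prompt notice of a new, unrelated death after the window closes.

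Fifth, the enrolment counts assume constant accrual, although the trial was interrupted and the rate after the restart is not given. Other timing sentences (7 working days to first infusion in section 8; surgery within 6 weeks of inclusion in section 1.2) would move the 49-day figure by about a week at most, or roughly one patient at the faster rate. The counts are ceilings, and the point does not depend on them.

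**Conclusion.** The concern holds. Sections 12.1.1 and 12.2 give different ends to AE and SAE reporting, and neither secures the 90 post-operative days that section 15.5 needs. On the likelier reading the shortfall is 0 to 4 days. On the one-month sentence it is about 60 of 90 days, with notification delayed by up to 93 to 152 days. Without a pause, the ceiling on patients entering meanwhile ranges from about 3 to about 22 across the cases shown; with a hold at 57 it is 0 to 6.

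This rests on reading the intervention as surgery, study treatment as durvalumab, surgery within 14 days of the last infusion and, for the enrolment counts, constant accrual. The harm is late detection of a death that should stop the trial, not loss of data: such deaths would still be recorded for overall survival. No endpoint, error rate or sample size is affected. It should be fixed, but it does not undermine the design.

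**What to change.** **Main change.** Replace the two windows with one. All SAEs and all deaths from any cause would be notified on the existing 24-hour timeline, from consent until the later of 100 days after the last infusion and 90 days after surgery. Keep the longer follow-up of drug-related events. Delete or align the one-month sentence in section 12.1.1, and name this window in section 12.3 as the observation period. Taking the later of the two dates removes the shortfall however long surgery is delayed.

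**Backstop.** Add a brief vital-status check, by call or record, at post-operative day 90 for the patients under the section 15.5 rule and the 57-patient review. The check supports prompt notification and does not replace it.

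The stopping criterion and the 30-day post-operative endpoint stay as they are.

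**Cost.** Amendment wording, at most 57 short checks (by record for patients already past day 90), and slightly more SAE reporting between one month after surgery and day 90.
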